In order to inhibit the enzymatic activity and increase the longevity of the bond, several materials have been investigated during the last 15 years (i.e. proanthocyanidin, genipin, tannic acid, chitosan, carbodiimide, glutaraldehyde, and chlorhexidine

GLUMA desensitizer, a solution containing glutaraldehyde (GA) and hydroxyethyl methacrylate (HEMA), is widely used to reduce sensitivity by occluding dentinal tubules and stabilizing collagen fibrils (Schupbach *et al.*, 1997)⁶. However, the ideal timing of GLUMA application in different adhesive protocols remains uncertain, raising questions about its effect on postoperative sensitivity, adhesive bond strength, and long-term restoration success.

Few studies Sayed ME *et al* 2022⁷ found that application of desensitizing agents on the prepared tooth surface for Class I cavity preparation for composite restoration reduces post- operative sensitivity where Gluma desensitizer found to reduce post-operative sensitivity when they were subjected to various stimuli such as cold drinks, intake of hot drinks, and intake of sugar for different periods of time which was scored based on the VAS (Visual Analog Scale). However the research done by Sancakli HS *et al* 2014⁸ found that no statistical differences were found with regard to post- operative sensitivity for occlusal composite restorations using different adhesive systems.

This clinical trial aims to evaluate the effectiveness of GLUMA in controlling the immediate post treatment sensitivity following occlusal composite restorations. In addition, to compare the difference between the

bonding systems (Etch-and-rinse & Self-etch) on reduction of post restoration sensitivity with or without Gluma desensitizer.

Primary Research question: Does application of Gluma desensitizer effectively reduces post-operative sensitivity following occlusal composite restoration?

For this clinical trial, a sample size of 504 restorations was calculated to be sufficient for detecting statistical difference using G* power software (α probability error – 0.05 and effect size – 0.2).

The intervention of this clinical trial is application of GLUMA Desensitizer (Heraeus Kulzer GmbH, Wehreim, Germany) which is currently available in the market as a aqueous solution containing Purified water, 35% hydroxyethyl methacrylate (HEMA), 5% glutaraldehyde, and pyrogenic silicic.

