Acid Etchant: 37% Phosphoric acid (Prime Dental Products Pvt Ltd.,)

Bonding agent: Te-Econom Bond" is Ivoclar Vivadent,

Composite (Charisma Smart, Kulzer GmbH, Germany),

Gluma Desensitizer (Kulzer GmbH, Germany).

The agents used are **Self Etch groups (Arm 4- Arm 6)** are,

Bonding agent: 3M ESPE Single Bond Universal Adhesive, Germany

Composite (Charisma Smart, Kulzer GmbH, Germany),

Gluma Desensitizer (Kulzer GmbH, Germany).

Intervention Type: Drug used in this clinical trial is Gluma Desensitizer (Kulzer GmbH, a German company).

Description: Caries excavation was done using diamond burs (Mani Co., Tochigi, Japan) with water coolant. Extent of caries excavation was done until sound hard or firm discolored or non-discolored dentin was achieved. Extent of caries excavation was assessed by an Experienced Post Graduate Supervisor (EPGS) blinded to treatment allocation group. Those teeth with width of the cavity preparation were no more than 1/3rd of the inter-cuspal width were included. Radiographs (Durr PSP Sensor, Durr, Germany) are taken to assess the depth of the preparation and Remaining Dentin Thickness (RDT). Two RDT measurements from mesial and distal pulp horn to floor of the preparation were calculated. Mean RDT was derived from the two readings. Preparation extending beyond the middle third of the dentin or with pulp exposure is excluded from the study. Radiograph assessment was done by EPGS. Teeth were excluded from the study if

they had pulp exposure or a prepared cavity that did not

meet standardization requirements.

Intervention description for Arm 1 (**Total Etch Control group (No desensitizer application)**) after cavity preparation, Total-etch adhesive was applied in the following way: 37% Phosphoric acid (Prime

Dental Products Pvt Ltd.,) was applied for 20 s on the prepared cavity. The acid was then washed by air and water pressure through a triple syringe for 20s. The surface was lightly air-dried. Then two coats of primer-bond solution (Te-Econom Bond, Ivoclar Vivadent) were applied by scrubbing with a micro brush, for 20 s per coat. When the surface became shiny, it was light-cured for 20s (Woodpecker LED, Guilin, China). After curing the adhesives, the light-cured nano-composite (Charisma Smart, Kulzer GmbH, Germany) was used for the restoration which was applied in increments (1–2 mm thick) by layering technique to reduce polymerization shrinkage.

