The Kruskal-Wallis test is a non-parametric statistical test used to determine if there's a significant difference between the medians of three or more independent groups. It's an alternative to the one-way ANOVA when the data doesn't meet the assumptions of normality or equal variances.

STATISTICAL ANALYSIS OVERVIEW:

This present study contains six arms whose descriptions have been provided in the brief summary. The statistical analysis was performed using IBM SPSS version 23. The normality was assessed using Shapiro – wilks test and Q -Q plots. Since the groups do not follow the normal distribution Kruskal – Wallis test to test the statistical significance of post operative sensitivity among the groups. Mann – whitney U test was used to assess the post operative sensitivity among the control groups.

GROUPS INVOLVED:

CONTROL GROUPS:

GROUP 1: Total Etch (TE) Control Group

GROUP 2: Self Etch (SE) Control Group

TEST GROUPS:

GROUP 2: TE - GLUMA Application After Acid Etching

GROUP 3: TE - GLUMA Application Prior to Acid Etching

GROUP 5: SE - GLUMA Application Prior to Acid Etching

GROUP 6: SE - GLUMA Application After Acid Etching

NULL HYPOTHESIS:

The null hypothesis states that there is no statistically significant difference in post operative sensitivity on GLUMA application etching before or after total etching or self-etching followed by composite restoration of the carious teeth.

SAMPLE SIZE CALCULATION:

For this clinical trial, a sample size of 504 restorations was calculated to be sufficient for detecting statistical difference using G* power software (α probability error – 0.05 and effect size – 0.2).

TYPE OF ANALYSIS:

The type of trial is a Noninferiority trials. By definition a non – inferiority trial tests whether a new experimental treatment is not unacceptably less efficacious than an active control treatment already in use. With continuous improvements in health technologies, standard care, and clinical outcomes, the incremental benefits of newly developed treatments may be only marginal over existing treatments. (Hahn S. Understanding noninferiority trials. Korean journal of pediatrics. 2012 Nov 23;55(11):403.)

This test is a non - inferiority trial hence the six groups have GLUMA application before etching of a composite restoration which is not unacceptably less efficacious in reducing post operative sensitivity in composite restoration of a carious tooth.

PROCEDURE:

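### Bonding class and adhesive product are completely aliased, and neither the only specified pairwise test nor the only interval estimate compares Gluma with no Gluma within one bonding system

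*Combined protocol and SAP*

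**What the plan says.** The second aim (Brief Summary and Detailed Description) is to compare the "bonding systems (Etch-and-rinse & Self-etch) on reduction of post restoration sensitivity with or without Gluma desensitizer". It names two generic classes and no product. The primary research question, also in the Detailed Description, is whether Gluma reduces sensitivity after an occlusal composite restoration.

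The lists of agents under Arm information fix one adhesive per class. For the total-etch arms (1-3) they give "Acid Etchant: 37% Phosphoric acid (Prime Dental Products Pvt Ltd" and "Bonding agent: Te-Econom Bond". For the self-etch arms (4-6) they give "Bonding agent: 3M ESPE Single Bond Universal Adhesive, Germany" and no separate acid. The composite is common to all six arms: "Composite (Charisma Smart, Kulzer GmbH, Germany". Application of the adhesive is also matched. Arm 1, for example, has "two coats of primer-bond solution (Te-Econom Bond, Ivoclar Vivadent) were applied by scrubbing with a micro brush, for 20 s per coat", and the self-etch arms have the same number of coats, scrubbing time and 20 s cure.

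The SAP null hypothesis is likewise generic, referring to "GLUMA application etching before or after total etching or self-etching followed by composite restoration of the carious teeth". The Brief Summary mentions Kruskal-Wallis and Mann-Whitney tests without naming contrasts. The SAP overview then restricts the latter: "whitney U test was used to assess the post operative sensitivity among the control groups". The only effect estimate with a confidence limit is a one-week mean difference of 0.18 between self-etch Gluma-prior (Arm 5) and total-etch Gluma-after (Arm 3).

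Arm numbers here follow the protocol's arm list. The SAP's group list numbers some arms differently.

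**The concern.** Each class is represented by one product, and neither product appears under both classes. A difference between Arms 1-3 and Arms 4-6 may therefore come from the acid step, from the adhesive, or from both. The introduction counts adhesive protocols that seal dentin poorly among the things that worsen sensitivity. It speaks of protocols and not of brands, but it makes the adhesive a plausible rival explanation on the trial's own reasoning. The documents neither limit the second aim to the two products nor list this as a limitation.

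The analysis makes this matter more. The six-group Kruskal-Wallis test does not say which arms differ. The two results that single out a pair of arms both cross systems: control v control contains no Gluma, and Arm 5 v Arm 3 has Gluma on both sides. The non-inferiority reading in the SAP Procedure section sets the other five arms against Arm 5, so three of those five comparisons (Arms 1-3) cross systems as well. A reader who looks for the effect of Gluma finds no pairwise estimate of it, and may take a contrast of two packages as an answer about Gluma or about bonding classes.

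**Working it through.** **1. The plan's own figure.** The one-week means in the SAP table are 0.26 (Arm 3) and 0.08 (Arm 5), and 0.26 - 0.08 = 0.18. With the stated dispersion of 0.1077 for the difference, the one-sided 95% lower limit is 0.18 - 1.645 × 0.1077 = 0.18 - 0.177 = 0.003. Both agree with the SAP. The arithmetic is not in question; the choice of contrast is.

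**2. Layout, from the arm descriptions.**

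| Arm | Separate acid | Adhesive | Gluma |
|---|---|---|---|
| 1 | yes | Te-Econom Bond | none |
| 2 | yes | Te-Econom Bond | before acid |
| 3 | yes | Te-Econom Bond | after acid |
| 4 | no | Single Bond Universal | none |
| 5 | no | Single Bond Universal | before adhesive |
| 6 | no | Single Bond Universal | after adhesive |

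**3. What cannot be separated.** Write the arm mean as a + b·class + c·product + d·(Gluma prior) + e·(Gluma after). The class and product columns are identical in every row, so their correlation is 1.0 and the five columns have rank 4. Adding the Gluma interactions with each gives rank 6 for 9 columns. Only the sum b + c can be estimated. For example, the one-week control difference is 0.12 - 0.21 = -0.09. It fits b = 0 with c = -0.09, b = +0.10 with c = -0.19, or b = -0.20 with c = +0.11. More restorations would estimate the sum more precisely but would not split it.

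**4. What can be estimated.** Without the product column, the class-by-timing model has rank 6 for 6 columns. Gluma contrasts within a system and the contrast of the two packages are therefore both estimable.

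**5. What 0.18 contains.** Arm 3 and Arm 5 differ in etching, product and Gluma timing. The difference can be routed through other arms (one-week means):

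- Through the controls: (Arm 3 - Arm 1) + (Arm 1 - Arm 4) + (Arm 4 - Arm 5) = (0.26 - 0.21) + (0.21 - 0.12) + (0.12 - 0.08) = 0.05 + 0.09 + 0.04 = 0.18. The cross-system step is 0.09.
- Through Arm 6: (0.26 - 0.21) + (0.21 - 0.08) = 0.05 + 0.13 = 0.18. The cross-system step is 0.05.
- Through Arm 2: (0.26 - 0.23) + (0.23 - 0.08) = 0.03 + 0.15 = 0.18. The cross-system step is 0.15.

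The cross-system part is between 0.05 and 0.15 according to the route, so no split is unique. On the route through the controls, half of 0.18 is a difference between two arms that received no Gluma.

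**6. Contrasts that bear on the primary question.** Differences in SAP table means, Gluma minus own control (negative favours Gluma):

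| Contrast | 24 h | 48 h | 1 week |
|---|---|---|---|
| Arm 2 - Arm 1 | 0.49 - 0.37 = +0.12 | 0.40 - 0.37 = +0.03 | 0.23 - 0.21 = +0.02 |
| Arm 3 - Arm 1 | 0.28 - 0.37 = -0.09 | 0.28 - 0.37 = -0.09 | 0.26 - 0.21 = +0.05 |
| Arm 5 - Arm 4 | 0.20 - 0.66 = -0.46 | 0.03 - 0.41 = -0.38 | 0.08 - 0.12 = -0.04 |
| Arm 6 - Arm 4 | 0.61 - 0.66 = -0.05 | 0.37 - 0.41 = -0.04 | 0.21 - 0.12 = +0.09 |

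These are rounded and descriptive, without adjustment. Arm 5 also began lower than Arm 4 (pre-operative means 0.63 and 1.88), so its early differences are not a clean Gluma effect either. At one week the Gluma mean is below its control in one contrast of four.

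**The case against.** The strongest reply is that a bonding system can reasonably mean the package of etchant and adhesive. Both packages are fully named, and arms were allocated at random, so the second aim is answered for those two packages. This stands. A reader might infer that the second aim cannot be answered at all; the documents do not support that. What fails is generalisation to etch-and-rinse and self-etch as classes. The aim invites it, because its parenthesis names classes only.

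A second reply is that the SAP draws conclusions about named groups and does not expressly credit 0.18 to Gluma or to timing. This also stands. A reader might infer that the SAP presents 0.18 as a Gluma effect, but its text says only that one named group had less sensitivity than another. The difficulty is that no within-system Gluma v control estimate stands beside it. Choosing a contrast that changes both system and timing would be a problem even with a single product throughout.

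Third, the null hypothesis mainly concerns the timing of Gluma and is not clearly a hypothesis of one system against the other. The case for rewriting it on this ground is weak.

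Two figures are tempting and should not be used. A reader might infer that product explains between 0 and 100% of a system difference. If product and class act in opposite directions, the share can be negative or exceed 100%, as the examples in step 3 show. A reader might also size the aliasing from the SAP's N column as 86 + 94 + 86 = 266 against 82 + 80 + 76 = 238 analysed restorations. The SAP's mean ranks do not fit those counts. Weighted by the listed N, they average 126.5 for the six groups (pre-operative and 24 h) and 42.5 for the two controls. Ranks of N units average (N + 1)/2, so these fit 252 and 84 units, not 504 and 168. Aliasing is complete whatever the counts.

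**Conclusion.** The point holds as a limit on interpretation and as a gap in the analysis. Aliasing of class and product is total. Cross-system contrasts compare phosphoric acid plus Te-Econom Bond with Single Bond Universal used without separate acid, and nothing broader. The control v control test and the 0.18 estimate both cross systems, and neither answers the question of Gluma v no Gluma.

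The design itself can still answer the primary question, since contrasts within a system are unaffected by the aliasing. The conclusion rests on the arm descriptions alone. It does not assume that either adhesive could be used in the other mode, that the products differ in performance, or any particular analysed sample size.

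**What to change.** 1. Answer the primary question with Gluma v control contrasts within each system: Arms 2 and 3 v Arm 1, and Arms 5 and 6 v Arm 4, with estimates and intervals and a stated rule for multiplicity. Results are already in the document, so label contrasts added now as post hoc. Handle the pre-operative imbalance as its own issue.
2. Do not use the 0.18 difference as evidence of a Gluma, timing or bonding-class effect. If it is kept, describe it as a comparison of two named arms that differ in all three respects.
3. Word the second aim and any cross-system conclusion as a comparison of the two named packages, and state the aliasing as a limitation.

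No new data and no clinical change are needed. The main downside is a narrower claim about bonding systems. Within-system contrasts are also less powerful than they may appear from the total of 504. Assuming 84 per arm as planned, a standardised difference of 0.4 and an unadjusted two-sided 0.05 level, power is Φ(0.4 × √(84/2) - 1.96) = Φ(0.63) = 0.74 by the normal approximation.

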COVER PAGE

Official title of the study: Efficacy of Gluma desensitizer in controlling the immediate post treatment sensitivity in etch-and-rinse and self-etch adhesive occlusal composite restorations

NCT04248803

Date of the document: 02-09-2025

Efficacy of Gluma desensitizer in controlling the immediate post treatment sensitivity in etch-and-rinse and self-etch adhesive occlusal composite restorations

NCT04248803

BRIEF SUMMARY

Background

One of the most widely used esthetic restorations in dentistry is composite. Despite the indispensable value that composite brings to a dentist's arsenal, the postoperative sensitivity following composite resin restorations are an undesirable outcome often leading to patient discomfort.

GLUMA desensitizer, a solution containing glutaraldehyde and hydroxyethyl methacrylate (HEMA), is widely used to reduce sensitivity by occluding dentinal tubules and stabilizing collagen fibrils. However, the ideal timing of GLUMA application in different adhesive protocols remains uncertain, raising questions about its effect on postoperative sensitivity, adhesive bond strength, and long-term restoration success.

This clinical trial aims to evaluate the effectiveness of GLUMA in controlling the immediate post treatment sensitivity following occlusal composite restorations. In addition, to compare the difference between the bonding systems (Etch-and-rinse & Self-etch) on reduction of post restoration sensitivity with or without Gluma desensitizer.

Sample Size, Blinding and Randomization

For this clinical trial, a sample size of 504 restorations was calculated to be sufficient for detecting statistical difference using G* power software (α probability error – 0.05 and effect size – 0.2).

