The primary outcome of this clinical trial is to evaluate the effectiveness of GLUMA in controlling the immediate post treatment sensitivity following occlusal composite restorations. Hence, all the patients were assessed for post restoration sensitivity after 24 hours, 48 hours and at the end of one week. The secondary outcome was to assess whether patient had post-operative sensitivity due to any trigger stimulus. This was also assessed at the end of 24 hours, 48 hours and one week post-operatively.

Post-operative sensitivity and trigger factors (if any) after 24 and 48 hours were assessed with VAS score (1- 10) through telephonic call by a resident student who are unaware of the treatment allocation group. In this study a 1-10 scale were used and the patient is asked to choose a number ranging from 1 to 10 based on their sensitivity, with 1 being the least sensitivity and 10 being the most.

Post-operative sensitivity and trigger factors (if any) after one week were checked by recalling and clinically assessing the patients using Schiff cold air sensitivity scale by a blinded EPGS.

Statistical Analysis

Data was assessed (IBM SPSS Version 23, USA) for normality using the Shapiro-Wilk test. Non-parametric Kruskal-Wallis test and Mann Whitney U test are employed for difference in post treatment sensitivity score among the different groups.

DETAILED DESCRIPTION

Introduction One of the most widely used esthetic restorations in dentistry is composite. Despite the indispensable value that composite brings to a dentist's arsenal, the postoperative sensitivity following composite resin restorations are an undesirable outcome often leading to patient discomfort. ¹This sensitivity

is primarily caused by dentinal fluid movement within exposed tubules, which can be exacerbated by adhesive protocols that do not adequately seal the dentin (Pashley *et al.*, 2002)², micro gaps caused by polymerization shrinkage (Loguercio *et al.*, 2004)³, dentin desiccation and bond degradation over time, potentially due to matrix metalloproteinase (MMP) activation (Mazzoni A *et al.*, 2015)⁴. It's been reported that during the first week after placement of Class I posterior composite restorations, 23% of the patients experienced post-operative sensitivity.⁵

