Post –operative sensitivity after 24 and 48 hours were assessed with VAS score (1- 10) through telephonic call by a resident student who are unaware of the treatment allocation group. The Visual Analogue Scale (VAS) is a common and effective tool for assessing pain and other subjective symptoms, including postoperative sensitivity. In this study a 1-10 scale were used and the patient is asked to choose a number ranging from 1 to 10 based on their sensitivity, with 1 being the least sensitivity and 10 being the most. The advantages of VAS scale is its simplicity, ease of use and applicability.

Post-operative sensitivity after one week all the patients were recalled and clinically assessed by Schiff cold air sensitivity scale by an Experienced Post Graduate Supervisor (EPGS) who is unaware of the allocated treatment groups and those patients with post-operative sensitivity of VAS > 3 were considered for the results (Berkowitz G *et al* 2013)¹¹. A statistician also looked at the treatment results without knowing anything about them.

Schiff cold air sensitivity scale is used to check for post-operative sensitivity which measures a patient's response to a cold air stimulus, helping to gauge the level of sensitivity in a tooth. The procedure involves directing a stream of air at the tooth and observing the patient's reaction, with scores ranging from no response to severe pain (intensity) requiring immediate discontinuation of the stimulus.

The secondary outcome was to assess whether patient had post-operative sensitivity due to any trigger stimulus. This was assessed at the end of 24 hours, 48 hours and one week post-operatively. At 24 hours and 48 hours through telephonic call a resident student who is unaware of the treatment allocation group questioned the patients those who had post-operative sensitivity whether the sensitivity is due to any stimuli (upon mastication/ intake of hot or cold) or spontaneous.

At the end of one week the patients were recalled checked for post-operative sensitivity using both Schiff Air Scale and those patients with post-operative sensitivity of VAS > 3 were questioned whether sensitivity is due to any stimuli¹¹ (upon mastication/ intake of hot or cold) or spontaneous.

STATISTICAL ANALYSIS PLAN

DEFINITION:

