All statistical analyses were performed using non-parametric tests due to the non-normal distribution of the data, as confirmed by both the **Kolmogorov–Smirnov** and **Shapiro–Wilk** tests

($p < 0.001$). Descriptive statistics including mean and standard deviation (Mean \pm SD) were calculated for each of the six desensitizer groups at different time points: Pre-operative, 24 hours, 48 hours, and 1 week post-operative sensitivity, measured using the Visual Analog Scale (VAS).

For intergroup comparisons across all six desensitizer protocols, the **Kruskal–Wallis test** was used independently for each time point. This non-parametric method was selected to assess statistically significant differences in median VAS ranks among the groups, given the violation of normality assumptions. A separate p -value was generated for each time point:

- Pre-operative VAS: $p = 0.003$ (significant)
- 24-hour VAS: $p = 0.126$ (not significant)
- 48-hour VAS: $p = 0.050$ (borderline)
- 1-week VAS: $p = 0.013$ (significant)

Pairwise comparisons between the **Total-etch control** and **Self-etch control** groups were performed using the **Mann–Whitney U test**. This analysis revealed a statistically significant difference in pre-operative VAS scores ($p = 0.012$), while post-operative scores showed no significant differences at 24 hours ($p = 0.337$).

Mean pain scores (VAS) were also summarized for each group at all four-time intervals. The **self-etch Gluma prior to etching group consistently showed the lowest VAS scores** at all time points, suggesting reduced post-operative sensitivity in this group.

Given the minimal differences in outcome scores among the other groups, and the slightly better performance of the self-etch GLUMA prior to etching group, the data suggest that **most treatment protocols were non-inferior** to the best-performing group. Therefore, the trial was interpreted as

a **non-inferiority study**, evaluating whether the other etching and desensitizing protocols were not clinically worse than the most effective group.

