A significance level of $p < 0.05$ was considered statistically significant throughout the analysis. In the present study, the Kruskal-Wallis test was used to compare six desensitizer groups at different time intervals (Pre-operative, 24 hours, 48 hours, and 1 week post-operatively) based on Visual Analog Scale (VAS) scores. Since each time point represents a distinct clinical endpoint, a separate Kruskal-Wallis test was conducted for each, yielding **individual p-values** corresponding to each time point. As the Kruskal-Wallis test does not permit aggregation of multiple outcomes into a single p-value, **a common p-value is not statistically appropriate**.

Ranks

	Desensitizer Group	N	Mean Rank	P Value ^a
Pre Op VAS	Total etch control	86	105.48	0.003
	Total etch Gluma prior to etching	94	141.70	
	Total etch Gluma after etching	86	116.12	
	Self etch control	82	142.30	
	Self etch Gluma prior to etching	80	106.20	
	Self etch Gluma after etching	76	147.55	
	Total	504		
Post Op sensitivity 24hr VAS	Total etch control	86	125.47	0.126
	Total etch Gluma prior to etching	94	122.94	
	Total etch Gluma after etching	86	117.62	
	Self etch control	82	136.49	

	Self etch Gluma prior to etching	80	125.30	
	Self etch Gluma after etching	76	132.62	
	Total	504		
Post Op sensitivity 48hr VAS	Total etch control	86	131.74	0.050
	Total etch Gluma prior to etching	94	127.98	
	Total etch Gluma after etching	86	123.48	
	Self etch control		132.76	
	Self etch Gluma prior to etching	80	114.36	
	Self etch Gluma after etching	76	128.18	
	Total	504		
Post Op sensitivity 1 week VAS	Total etch control	86	124.24	0.013
	Total etch Gluma prior to etching	94	130.96	
	Total etch Gluma after etching	86	124.38	
	Self etch control	82	129.76	
	Self etch Gluma prior to etching	80	115.00	
	Self etch Gluma after etching	76	134.53	
	Total	504		

p < 0.05 denotes statistically significant difference. All the values exhibit non – statistically significant difference. Statistical test applied *

Kruskal – Wallis test

Ranks

	Desensitizer Group	N	Mean Rank	*P Value
Pre Op VAS	Total etch control	86	36.83	0.012
	Self etch control	82	48.45	

	Total	168		
Post Op sensitivity 24hr VAS	Total etch control	86	40.67	0.337
	Self etch control	82	44.41	
	Total	168		

p< 0.05 denotes statistically significant difference. All the values exhibit non – statistically significant difference except the pre operative pain scores. Statistical test applied * Mann Whitney U test

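### The SAP specifies no comparison of a Gluma arm with the no-Gluma control of its own adhesive, so the primary question has no planned contrast.

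*Combined protocol and SAP*

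**What the plan says.** The Detailed Description states the primary research question as "Does application of Gluma desensitizer effectively reduces post-operative sensitivity following occlusal composite restoration". A further aim is "to compare the difference between the bonding systems (Etch-and-rinse & Self-etch) on reduction of post restoration sensitivity with or without Gluma desensitizer". Arm 1 is the no-Gluma control for total etch and Arm 4 the no-Gluma control for self etch.

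The analysis text is spread over several places:

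- Brief Summary, Statistical Analysis: "Mann Whitney U test are employed for difference in post treatment sensitivity score among the different groups". No pair is named.
- SAP, Statistical Analysis Overview: Kruskal-Wallis across the groups, then "Mann – whitney U test was used to assess the post operative sensitivity among the control groups".
- SAP, Procedure: a separate six-arm Kruskal-Wallis test at each time, with no post-hoc procedure, and a Mann-Whitney test of total-etch control against self-etch control. The second Ranks table gives that pair pre-operatively and at 24 h only.
- SAP, Estimated Value: one difference with a confidence limit, 0.18 at 1 week, self-etch Gluma-prior against total-etch Gluma-after.
- SAP, Type of Analysis: "The type of trial is a Noninferiority trials", defined against an active control already in use. The Procedure instead takes the best-performing arm as reference, "evaluating whether the other etching and desensitizing protocols were not clinically worse than the most effective group". No margin is given.

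**The concern.** None of these analyses isolates Gluma. A six-arm omnibus result cannot be attributed to Gluma, its timing or the adhesive. The Mann-Whitney test compares two arms that both lack Gluma. The 0.18 compares two arms that both received it and that differ in adhesive and timing together. Followed as written, the SAP yields no estimate, interval or p-value for Gluma against no Gluma in either adhesive.

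The Procedure still reads the low scores of self-etch Gluma-prior as a sign of reduced sensitivity. That arm began 1.25 points below its own control (0.63 v 1.88), so low post-operative scores alone do not show an effect of Gluma.

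**Working it through.** **1. The plan's own estimate.** From the means table, 0.26 - 0.08 = 0.18. With SDs 0.95 and 0.27 and 84 per arm, SE = sqrt(0.95²/84 + 0.27²/84) = 0.108, against the printed 0.1077. The one-sided limit is 0.18 - 1.645 × 0.1077 = 0.003, as printed. The figure reproduces, but it is a Gluma-against-Gluma contrast.

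**2. The missing contrasts, unadjusted.** Inputs are the tabulated means and SDs and the N in the first Ranks table (86, 94, 86, 82, 80, 76). SE = sqrt(sd1²/n1 + sd2²/n2), with Welch 95% intervals. Each entry is the Gluma arm minus its own control.

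| Contrast | 24 h | 48 h | 1 week |
|---|---|---|---|
| Total-etch prior | +0.12 (-0.23 to 0.47) | +0.03 (-0.29 to 0.35) | +0.02 (-0.21 to 0.25) |
| Total-etch after | -0.09 (-0.39 to 0.21) | -0.09 (-0.39 to 0.21) | +0.05 (-0.21 to 0.31) |
| Self-etch prior | -0.46 (-0.77 to -0.15) | -0.38 (-0.60 to -0.16) | -0.04 (-0.13 to 0.05) |
| Self-etch after | -0.05 (-0.46 to 0.36) | -0.04 (-0.35 to 0.27) | +0.09 (-0.05 to 0.23) |

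With N halved (see step 4), self-etch prior becomes -0.90 to -0.02, -0.70 to -0.06 and -0.17 to 0.09. The data are strongly skewed, so all these intervals are approximate.

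**3. Baseline.** Pre-operative differences, Gluma minus own control, are +0.86 (1.72 - 0.86), +0.30 (1.16 - 0.86), -1.25 (0.63 - 1.88) and +0.23 (2.11 - 1.88). Adjusted difference = unadjusted difference - r × (pooled post SD / pooled pre SD) × pre-operative difference. The pre/post correlation r is not reported, so 0.2, 0.4 and 0.6 are assumptions. Pooled pre SDs are 1.936, 1.881, 1.763 and 2.323. Pooled post SDs, in the same order, are 1.204, 0.992, 0.993 and 1.315 at 24 h; 1.087, 0.992, 0.720 and 0.986 at 48 h; and 0.791, 0.865, 0.302 and 0.438 at 1 week. Example, self-etch prior at 24 h with r = 0.4: -0.46 + 0.4 × (0.993/1.763) × 1.25 = -0.18.

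| Contrast, r = 0.2 / 0.4 / 0.6 | 24 h | 48 h | 1 week |
|---|---|---|---|
| Total-etch prior | 0.01 / -0.09 / -0.20 | -0.07 / -0.16 / -0.26 | -0.05 / -0.12 / -0.19 |
| Total-etch after | -0.12 / -0.15 / -0.19 | -0.12 / -0.15 / -0.19 | 0.02 / -0.01 / -0.03 |
| Self-etch prior | -0.32 / -0.18 / -0.04 | -0.28 / -0.18 / -0.07 | 0.00 / 0.05 / 0.09 |
| Self-etch after | -0.08 / -0.10 / -0.13 | -0.06 / -0.08 / -0.10 | 0.08 / 0.07 / 0.06 |

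Seven of the 12 contrasts favour Gluma unadjusted; 8, 10 and 10 do so at r = 0.2, 0.4 and 0.6. For self-etch prior with printed N, the 24 h and 48 h intervals exclude zero at r = 0.2 (-0.64 to -0.001; -0.51 to -0.05) and include it at 0.4 (-0.48 to 0.12; -0.39 to 0.04) and 0.6. With N halved they include zero at all three.

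**4. N must be settled first.** The weighted mean of the six mean ranks is 126.5 at every time, so N = 2 × 126.5 - 1 = 252, not 504. The control pair averages 42.5, so N = 84, not 168.

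The printed p-values do not agree on one N. Take whole-number scores with 0 for none. At 48 h, 0.03±0.16 in 40 is a single score of 1, and the arm's mean rank of 114.36 then gives 222 zeros overall. At 1 week the mean rank of 115.00 equals (229 + 1)/2, giving 229 zeros. The tie-corrected six-arm p is then 0.355 (48 h) and 0.207 (1 week) on 252 rows, but 0.050 and 0.013, as printed, on 504 doubled rows. The pre-operative p of 0.003 and the control-pair p of 0.012 and 0.337 cannot come from doubled rows, which allow at most about 0.00002, 0.002 and 0.318; they fit single rows.

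**5. The 1-week cell and scale.** In the means table 0.08±0.27 is 3 scores of 1 in 40, and 0.12±0.33 is 5 in 41. Let Z be the zeros overall and y the rank of a score of 1. Solving 37(Z+1)/2 + 3y = 40 × 115.00 with 36(Z+1)/2 + 5y = 41 × 129.76 gives y of about 406, which is impossible among 252. The mean rank of 115.00 fits no sensitivity at all in self-etch prior. The 0.18 uses this disputed cell. The scale also conflicts: Outcome measures has "Post-operative sensitivity after one week all the patients were recalled and clinically assessed by Schiff cold air sensitivity scale", while the Ranks table is headed "Post Op sensitivity 1 week VAS".

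**The case against.** The strongest reply is that the documents are not silent. The Brief Summary applies Mann-Whitney to the groups generally, the six-arm test includes both controls, and anyone can subtract the tabulated means. The last point stands: unadjusted contrasts are available and are shown above. What cannot be recovered is a baseline-adjusted contrast. The Brief Summary names no pair, and the SAP then narrows the test to the two controls.

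The non-inferiority text might be thought to supply the comparison. It does not: its two descriptions of the reference disagree, the reference actually used was picked from the results and is itself a Gluma arm, and there is no margin.

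It is also fair to say that one question could be answered by a single Gluma effect stratified by adhesive. That would be a legitimate summary. However, the after-etch application comes before the adhesive in Arm 3 and after the cured adhesive in Arm 6, so pooling mixes different procedures. The four contrasts are more direct.

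Two stronger readings are tempting. A reader might infer that baseline adjustment works against Gluma. With a positive pre/post correlation that is true only for self-etch prior; the other three arms started above their controls and move towards Gluma. A reader might also infer that every record was entered twice. The pre-operative and control-pair p-values rule out uniform doubling.

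**Conclusion.** The omission is real and must be fixed. It is established by reading the SAP and needs none of the arithmetic. The arithmetic shows that it matters: the reported 0.18 at 1 week does not represent any arm's difference from control, and self-etch prior differs from its own control at that time by only -0.04 (-0.13 to 0.05, printed N). Its unadjusted differences at 24 h and 48 h exclude zero, but whether they survive adjustment depends on an unreported correlation and on whether N is 504 or 252.

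The documents therefore do not show that Gluma works, and they do not show that it fails. The intervals rest on normal approximations to skewed data. The adjusted figures rest on assumed correlations and are roughest for self-etch prior at 48 h, where the two SDs are 0.16 and 1.00. The zero counts assume whole-number scores with 0 for none, although the stated scale starts at 1.

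**What to change.** 1. Reconcile first: N (504 or 252, and which rows each p-value used); the 1-week scale (Schiff or VAS); the Outcome measures rule that considers only patients with VAS above 3; and the 1-week self-etch prior cell, where the Ranks and means tables disagree.
2. Add four contrasts, named by treatment because the SAP group list uses GROUP 2 twice and swaps the total-etch order: total-etch Gluma-prior and total-etch Gluma-after, each against total-etch control; self-etch Gluma-prior and self-etch Gluma-after, each against self-etch control.
3. Analyse all four at 24 h, 48 h and 1 week by one rank-based or ordinal method, penalised so that arms with few non-zero scores can be fitted. Adjust for pre-operative VAS, give 95% CIs, and apply Holm over all 12 tests. A single primary time point can no longer be chosen without sight of the results.
4. Label the contrasts post hoc and report them as the answer to the primary question in place of the 0.18. Remove the non-inferiority conclusion, or state that it has no margin and a reference picked from the results.

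Cost: re-analysis of existing data and new SAP wording. Power per contrast falls. At an assumed standardised difference of 0.40, two-sample t-test power with 84 per arm drops from 73% at alpha 0.05 to 38% at Holm's first step (0.05/12 = 0.00417). With 42 per arm it drops from 44% to 14%. Post hoc status also limits what may be claimed.
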